## 6. STUDY PROCEDURES

### 6.1. Data Source

Patients using apixaban will be identified from the National Prescribed Drug Register (PDR) which contains information on all drugs prescribed in Sweden that are dispensed to patients outside hospitals, including information about patients, drugs by ATC codes, dates, settings of the dispensing, and the specialty of the prescribing physician.

Relevant clinical history for the apixaban users identified from the PDR will be obtained from the National Patient Register (NPR). Patients in the PDR who have used apixaban will be linked to the NPR by a personal identification number (PIN) unique to all Swedish citizens. The NPR contains data from all hospital admissions in Sweden from 1987 to present. At each discharge, information is collected about the patient's demographics, primary and secondary diagnoses, procedure codes, hospitals and wards of admission, and dates of admission and discharge. Patients who have undergone knee or hip replacement surgery will be identified by applicable procedure codes and relevant ICD-10 diagnostic codes. The ICD-10 classification system was used from 1997 and onwards so data on diagnoses and procedures may extend back to 1997.

Since 2001, it is also possible to collect the same information from visits to hospital outpatient offices. Information about other diagnoses (eg, atrial fibrillation) in patients admitted to the hospitals without knee or hip replacement or visiting hospital outpatient offices will also be retrieved. The register is updated annually and data from the previous year is usually available for analyses in November each year after completion of data quality checks.

The databases cover the whole Swedish population of 9.3 million inhabitants. In 2008, about 14,500 knee and hip replacement surgeries and 4,600 hemi-hip arthroplasties were performed; 78% of the procedures were performed for primary arthrosis. The number of primary TKA was 10,600 in 2008. In addition, re-operations and revisions were also performed. Following an average hospital stay of 4 days, 25% of the patients are discharged to rehabilitation centers or nursing homes and 75% of the patients are discharged to home. The total number of hip arthroplasties increased by 10% from 2008 to 2010.

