Inpatient and outpatient hospital data are available through the NPR, but the register does not include information from primary care visits. To address the missing primary care data, a sensitivity analysis will examine primary care records for apixaban users in Västra Götaland County (1.6 million, available from 2006). These regional data will supplement the nationwide data with greater detail for patients in Västra Götaland County, as well as provide an insight into the effect of missing primary care data. At this time, Västra Götaland is the only region in Sweden where primary care data are available. These records are based on patient contacts to primary care centers and collected in the health administrative databases.

The total number of persons diagnosed with atrial fibrillation and flutter in inpatient settings in 2010 was 25,672 (0.3%) according to national Swedish health statistics. The overall prevalence of atrial fibrillation has been studied in a geographically well-defined area of northern Sweden using data from a quality register of anticoagulant treatment and was found to be 2.5% in 2010 (Andersson, Londahl et al. 2012).

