### **6.3. Decision Rule for Defining On- and Off-label Use**

For the purpose of this study, apixaban prescriptions for the NVAF and treatment of DVT/PE indications will be considered off-label up to and including the date that apixaban received approval for those uses in the EU. Apixaban prescriptions for the NVAF and the treatment of DVT/PE indications will be classified as on-label starting on the day after regulatory approval and continuing through the end of the study.

On-label use of apixaban will be defined as a dispensation of the drug to:

1. An adult (ie, 18 years of age or older) and
2. A patient whose hospital records include:
  - a) An elective hip or knee replacement within 30 days before the apixaban prescription, or,
  - b) An apixaban prescription after 19 November 2012 and a diagnosis of NVAF before that apixaban prescription, or,
  - c) An apixaban prescription after 28 July 2014 and a diagnosis of DVT or PE before the apixaban prescription ([Figure 1](#)).

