#### 7.1. Sample Size Calculation

This is a descriptive study of drug usage without any pre-defined hypothesis to be tested. Therefore, no power calculation was performed. All individual patients identified to have received apixaban in the database in the study period will be included in the study without any sampling procedure.

Based on the Sponsor's projection of the number of patients using apixaban in 2012-2014 for prevention of VTE following a hip or knee replacement it is expected that approximately 600 patients will be included in the study. It is projected that up to 13,000 patients with atrial fibrillation (AF) may be included in the study.

As shown in the table below, 19,000 apixaban patients with any indication will provide sufficiently precise estimates of on-label use. For instance, if 25% of patients use apixaban off label, the width of the 95% CI for the off-label use percent will be 1.2 percent ([Table 2](#)).

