## 7.2. Data Analyses

Descriptive analyses of patient level data will be conducted. Patients will be classified as on-label or off-label apixaban users based on their first prescription for apixaban. The demographic and clinical characteristics of patients identified to have received an apixaban dispensation will be described. The proportion of patients receiving the drug for indications within and outside the approved label in each of the study years will be estimated and any trend over time will be described. From the hospital discharge records, the comorbidities and clinical procedures (e.g., surgeries) at the time of or within 30 days prior to the off-label use will be tabulated as the possible indications for the off-label use. If discharge records during this period do not provide possible indications, information from previous discharges will also be tabulated according to the most recent diagnosis. Furthermore, possible switching from other antithrombotic treatment will be investigated based on dispensed prescriptions during the past year. The dose and duration of prescriptions will be summarized where available.

Stratified descriptive analyses by indication will be performed as described below. As the first step, the study will estimate the proportions of all patients in Swedish databases over the 3-years post-launch period who received apixaban for:

1. VTE prevention following elective hip and knee replacement surgery (on-label indication).
2. NVAf (off-label indication before the approval, and on-label following the approval).
3. Treatment of DVT/PE (off-label indication before the approval, and on-label following the approval).
4. Any other conditions from a list of pre-defined off-label indications, including other types of surgery and history of other diseases (off-label indications). These may include but will not be limited to hip fracture surgeries, general surgeries, gynaecologic and abdominal surgeries, and diagnoses such as cancer, myocardial infarctions, other cardiac conditions, and other hypercoagulable states in which apixaban could be used off-label.

5. Patients who have no evidence of the conditions for on-label use and who cannot be assigned to the list of pre-defined off-label uses will be classified as off-label and unknown.

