The only available primary data is from patients in Västra Götaland County. Primary care data may contain information on the conditions that are used to classify on-label or off-label apixaban use. A sensitivity analysis will compare the proportion of on-label users based on both primary care and hospital data to the proportion of on-label use when only the hospital data is used among those in Västra Götaland County. This assumes that the availability of GP data is not related to the ratio of on-label or off-label use and that Västra Götaland County is representative of all of Sweden.

Second, descriptive analyses will be performed in each of the indication strata to summarize:

1. Demographic characteristics of patients and prescriber specialty.
2. Estimated duration of apixaban treatment and dosages used.
3. Concomitant medication use, with the focus on contra-indicated medications.
4. History of treatment with other anticoagulants.
5. Select co-morbid conditions/medical history, such as renal impairment, severe hepatic impairment, congenital or acquired bleeding disorders.

For off-label indication strata, distribution of surgical procedures and diagnoses that patients had prior to receiving apixaban to infer possible indications that apixaban was used for. For instance, counts and proportions of patients who had other orthopaedic surgery (eg, hip fracture), within 30 days of apixaban prescription will be reported.

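### Section 7.2 counts patients with no indication found as off-label, although primary care diagnoses exist for one county only, and the county check is never applied to the national figure

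*Protocol*

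**What the plan says.** Objective 1 (section 2) is to estimate the proportion of outpatient apixaban users treated for approved indications. Section 7.2 sorts patients into five groups. Items 1 to 3 are the approved indications, with items 2 and 3 off-label before their approval dates. Item 4 is a list of pre-defined off-label conditions, including other surgery and a history of other diseases. Item 5 takes everyone left: those who "cannot be assigned to the list of pre-defined off-label uses will be classified as off-label and unknown".

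The evidence for an indication comes from the National Patient Register, of which section 6.1 says that "the register does not include information from primary care visits". The same section adds that "Västra Götaland is the only region in Sweden where primary care data are available". Section 6.2 admits prescriptions from general practitioners as well as specialists. It also counts primary care diagnoses of NVAF and DVT/PE where they exist. Section 6.3 defines on-label use differently, through "A patient whose hospital records include" one of the listed conditions.

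The sensitivity analysis in section 7.2 compares the on-label proportion with and without primary care data among Västra Götaland patients. Its stated basis is: "This assumes that the availability of GP data is not related to the ratio of on-label or off-label use", together with the county being representative of Sweden. Section 10.2 concedes that indications may be missing in some cases.

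**The concern.** Under item 5, the absence of a record becomes a finding of off-label use. A patient whose NVAF or DVT/PE was diagnosed and treated entirely in primary care has no qualifying hospital record and cannot be on-label outside the county. Section 10.2 mentions missing indications but does not say that the classification rule turns them into off-label use, so that this error has a known direction.

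Three outputs are affected. The estimate for objective 1 mixes missing information with off-label prescribing. The description of off-label users for objective 2 would include misclassified on-label users. The yearly trend would shift if the share of patients diagnosed only in primary care changes over the study years.

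The county data could quantify the problem. As written, though, they yield two proportions for one county, and no step adjusts, bounds or re-reports the national proportion.

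**Working it through.** **The plan's own figure.** Table 2 gives 95% confidence interval widths for N = 19,000. The formula 2 × 1.96 × √(p(1 − p)/19,000) gives 0.62, 1.02, 1.23, 1.36 and 1.42 points at p = 5, 15, 25, 35 and 45%. The table states 0.6, 1.0, 1.2, 1.4 and 1.4, so it reproduces.

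**Coverage of primary care data.** 1.6/9.3 = 17.2% of the population (section 6.1), so 82.8% has none.

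**Size of this component.** Let T be the true on-label share and m the share of on-label users with no qualifying hospital record. Both are assumptions. Taking this error alone:

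- reported off-label = 1 − T(1 − m)
- excess over the true value = T × m

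| m | T = 75% | T = 85% | T = 95% |
|---|---|---|---|
| 2% | 1.5 points | 1.7 | 1.9 |
| 5% | 3.75 | 4.25 | 4.75 |
| 10% | 7.5 | 8.5 | 9.5 |
| 20% | 15 | 17 | 19 |

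Section 7.1 uses 25% off-label as its example, which corresponds to T = 75%. The excess equals the quoted 1.2-point width when m = 0.012/0.75 = 1.6%.

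**Sections 6.2 and 6.3.** If primary care diagnoses count wherever they exist, the excess arises only outside the county. If users follow population, it shrinks by the factor 0.828: at T = 75% and m = 10%, from 7.5 to 6.2 points. The county and the rest of Sweden would then be classified on different evidence.

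**Can the county support a correction?** If users follow population (an assumption), the county holds 0.172 × 19,000 ≈ 3,270 patients. Let q be the national hospital-only proportion not on-label, and r the county share of such patients whom primary care reclassifies as on-label. The corrected off-label proportion is q(1 − r), with approximate variance (1 − r)²q(1 − q)/19,000 + q²r(1 − r)/n, where n is the number of county patients not on-label by hospital data.

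Example with T = 75% and m = 10%:

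- q = 1 − 0.75 × 0.90 = 0.325
- r = 0.075/0.325 = 0.231
- n = 0.325 × 3,269 ≈ 1,062
- corrected proportion = 0.325 × 0.769 = 0.25, the true value
- variance = 6.8 × 10⁻⁶ + 17.7 × 10⁻⁶ = 24.5 × 10⁻⁶, so the standard error is 0.495 points and the width 1.9 points

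The uncorrected estimate would be 32.5%, with a width of 2 × 1.96 × √(0.325 × 0.675/19,000) = 1.3 points. The corrected interval is wider and contains the true value, provided that r carries over from the county to the rest of Sweden.

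**The case against.** Much of this is disclosed, and four stronger readings should be set aside.

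- *That 83% of patients are at risk of misclassification.* The figure is the population share without primary care data. Admissions and, since 2001, hospital outpatient visits are captured nationwide. Only on-label users never coded in either before the prescription are affected, so m could be small.
- *That the published off-label proportion is biased upward overall.* Only this component is known to push upward. Section 6.3 accepts any earlier NVAF diagnosis, while the indication in Table 1 requires one or more risk factors. That can classify off-label users as on-label. The net direction is unknown.
- *That undetermined patients are hidden, or that removing them gives a lower bound.* Item 5 is already a separate line, so the figure without it can be read from planned output. That figure is not a strict lower bound, because a missed NVAF patient with, for example, cancer or another cardiac condition falls into item 4.
- *That section 7.1 is wrong to say the sample "will provide sufficiently precise estimates of on-label use".* Table 2 reproduces and describes sampling error only. A sample size section need not cover misclassification.

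It is also fair to say that the representativeness assumption shows an intention to read the county result nationally, and that a SAP may give the calculation. That part of the objection stands: the missing step can be asserted only for this document. The off-label label in item 5, however, is fixed in the protocol, and section 7 requires major modifications to be reflected in an amendment.

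**Conclusion.** The concern holds in limited form. As written, the plan converts missing primary care diagnoses into off-label use, spread over items 4 and 5, and does not apply its own county check to the national proportion. The excess from this source is T × m. At T = 75% it reaches 1.2 points at m = 1.6% and 7.5 points at m = 10%; all of these T and m values are illustrative. The conclusion that this component pushes upward rests only on the stated rule and the stated data gap. Its size rests on m, which the county data can estimate. No claim about net bias is supported. Sections 6.2 and 6.3 also disagree on whether primary care diagnoses enter the main classification. Severity: should-fix.

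**What to change.** 1. Rename item 5 'indication not determinable'. Report the off-label proportion both without and with it, and do not present the former as a strict lower bound.
2. In Västra Götaland, estimate the share of all patients not on-label by hospital data (items 4 and 5 together) whom primary care reclassifies as on-label. Apply it to the rest of Sweden and report the corrected national proportion with an interval that includes the uncertainty in that share. Do this overall or in a few coarse strata, such as prescriber specialty and year; a full cross-classification of about 3,270 patients may be sparse.
3. Compare the hospital-only on-label proportion and the prescriber-specialty mix in the county with the rest of Sweden, so that representativeness is partly checked and not only assumed.
4. Reconcile sections 6.2 and 6.3 so that the main national classification uses the same evidence in every region, and check Figure 1 against the result.

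Cost: wording in sections 6 and 7.2 and a few more tables from data already planned, with no new data source. The corrected interval is wider (1.9 against 1.3 points in the example above), and the correction relies on one county's reclassification share holding elsewhere.

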## 6.2. Data Compilation Procedure

Patients who received a dispensation for apixaban (identified by ambulatory prescriptions by general practitioner or specialist physician) will be identified. The personal identification numbers of these patients will be used to link to their hospital records.

Hip and knee replacement and other surgeries will be identified via appropriate procedure codes and ICD-10 codes from hospital discharge diagnoses. The following algorithm will be used to identify the patients who have undergone the elective hip or knee replacement surgery:

- First, procedure codes will be used to identify all patients who have undergone hip or knee replacement surgery within 30 days before apixaban prescription (including total and partial replacement procedures).
- Second, hospital discharge diagnoses (both primary and secondary) will be used to see if these included hip or knee fracture diagnostic codes.
  - If yes, then the hip or knee replacement surgery will be considered non-elective and apixaban prescription off-label.

If the primary or secondary discharge diagnoses do not include hip or knee fracture, then surgery will be considered elective and apixaban prescription on-label.

NVAF and treatment of DVT/PE will be identified by ICD-10 diagnosis codes in the main or secondary discharge diagnoses as well as in hospital outpatient visits and, where available, the primary care diagnoses.

[figure not shown]

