## **10. STRENGTHS AND LIMITATIONS**

### **10.1. Strengths:**

- The study will use an established database that routinely collects information on the variables required to fulfill the objectives. There are strong linkage systems that utilize the unique national identifier of the patients to link different data sources. This database has been used for many pharmacoepidemiologic studies, including those looking at atrial fibrillation and orthopedic surgery populations (Weiss, Stark et al. 2006; Andersson, Londahl et al. 2012).

- The database has coverage of all age groups.
- The database has coverage of all hospital admission and discharge diagnoses.
- By repeating the annual analysis over a three-year period after launch of apixaban, the study will provide data on changing trends, if any.

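### The county check on missing primary care data is not split by year or indication, so it cannot show how far the yearly on-label series is distorted

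*Protocol*

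**What the plan says.** Section 7.2 classifies each patient by the first apixaban prescription and says that the on- and off-label proportions "in each of the study years will be estimated and any trend over time will be described". Section 10.1 lists the trend among the study's strengths: "By repeating the annual analysis over a three-year period after launch of apixaban, the study will provide data on changing trends, if any".

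On missing data, section 6.1 states that "the register does not include information from primary care visits". The remedy in section 7.2 is confined to one county: "A sensitivity analysis will compare the proportion of on-label users based on both primary care and hospital data". The comparator is the classification of the same county's users from hospital records alone. Two assumptions are attached. One is that the county represents Sweden. The other reads: "This assumes that the availability of GP data is not related to the ratio of on-label or off-label use". Neither concerns differences in capture between indications or between years.

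The indications come from different sources. For surgery, section 6.2 says that "procedure codes will be used to identify all patients who have undergone hip or knee replacement surgery within 30 days before apixaban prescription". For the medical indications, "NVAF and treatment of DVT/PE will be identified by ICD-10 diagnosis codes in the main or secondary discharge diagnoses", together with hospital outpatient visits and, only where available, primary care diagnoses. Under section 6.3, NVAF counts as on-label after 19 November 2012 and DVT/PE after 28 July 2014. Under section 7.2, a user with no evidence of an on-label condition is counted as off-label, either under a listed condition or as unknown.

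**The concern.** The error from missing primary care data runs one way, towards off-label, and falls almost wholly on NVAF and DVT/PE. By the decision rule it also depends on calendar time. Up to and including 19 November 2012 an AF user is off-label whether or not the diagnosis is found. A missed diagnosis can then move the user between off-label categories but cannot change on/off-label status. After that date the same missed diagnosis turns an on-label user into an off-label one. The same holds for DVT/PE around 28 July 2014.

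The yearly series therefore carries an error that changes from year to year, while the only planned check yields one difference for the county. What is at stake is the reading of the trend. Across the NVAF approval, the rise in on-label use that the rule itself creates would look smaller than it is. In later years, part of an apparent growth in off-label use could be an artefact of ascertainment.

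**Working it through.** **The plan's own figure.** Table 2 gives the full width of a 95% CI at 19,000 users. At 25% off-label, 2 × 1.96 × √(0.25 × 0.75 / 19,000) = 1.23 points, against 1.2 stated. The other four rows also reproduce (0.62, 1.02, 1.36 and 1.42 against 0.6, 1.0, 1.4 and 1.4). These widths are for all users together. A year with a third of them (6,333) would have a width of about 2.1 points at 25%, and a small first year a much larger one.

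**Mix of indications (section 7.1).** About 600 hip/knee users and up to 13,000 AF users are projected. Hip/knee is 600 / 13,600 = 4.4% of these two groups, so an unsplit county figure is almost wholly an AF figure.

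**Share of 2012 in which NVAF is on-label (section 6.3).** 20 November to 31 December is 42 days, and 42 / 366 = 11.5%.

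**Illustration.** The protocol does not give the following, so they are assumptions:
- 90% of users in every year have one of the labelled conditions, whether or not it was approved yet.
- w is the hip/knee share of these users: 60% in the first year, 2% in the last.
- Hospital data find all hip/knee surgery and a fraction s of AF.
- The remaining users are treated as AF, spread evenly over 2012. In the last year all of them are on-label.

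With a the fraction of AF use that is on-label by date:
- True on-label = 0.90 × [w + (1 − w) × a]
- Measured on-label = 0.90 × [w + (1 − w) × a × s]

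At s = 0.80:
- First year, a = 0.115: true 0.90 × (0.6 + 0.4 × 0.115) = 58.1%; measured 0.90 × (0.6 + 0.4 × 0.115 × 0.8) = 57.3%. Understated by 0.8 points.
- Last year, a = 1: true 90.0%; measured 0.90 × (0.02 + 0.98 × 0.8) = 72.4%. Understated by 17.6 points.
- True rise 31.9 points; measured rise 15.1 points.

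Varying s, with the rest fixed:

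| s | Understated, first year | Understated, last year | Measured rise (true 31.9) |
|---|---|---|---|
| 0.95 | 0.2 | 4.4 | 27.7 |
| 0.90 | 0.4 | 8.8 | 23.5 |
| 0.80 | 0.8 | 17.6 | 15.1 |
| 0.70 | 1.2 | 26.5 | 6.6 |

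**Within 2013-2014.** NVAF is on-label throughout. If the hip/knee share falls from 8% to 2% (assumed), the drift is 0.90 × (1 − s) × 0.06: 0.3 points at s = 0.95 and 1.6 at s = 0.70.

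**Can the county be split?** If users are spread by population (1.6 of 9.3 million), the county has 19,000 × 1.6 / 9.3 ≈ 3,270 users: about 2,240 with AF and 103 with hip/knee surgery. AF users spread evenly give about 750 a year, with a CI width of 4.3 points at 10%. Hip/knee gives about 34 a year, with a width of 20 points at 10%.

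**The case against.** The strongest objection is that subgroup cuts of a sensitivity analysis usually belong in the SAP, which is not shown. The county paragraph sits inside the indication-stratified step of section 7.2 and does not rule out strata. Section 7.3 also has the analysis run annually, although interim reports may omit parts of it. This has weight: a single unsplit comparison is the plain reading of the text, not an explicit statement. What remains is that the protocol defines the check and its assumptions, and neither matches the yearly trend that it promises.

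Second, a reader might infer that missing primary care data would create a false decline in on-label use, by about 10 points under the same assumptions: 0.90 × (w + (1 − w) × 0.8) falls from 82.8% to 72.4%. The documents do not support this. That formula counts first-year AF users as on-label, contrary to section 6.3. With the rule applied, the measured proportion rises from 57.3% to 72.4%. A measured fall across the approval needs more extreme inputs. For example, a hip/knee share falling from 90% to 2% with 70% capture gives 81.7% to 63.5%.

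Third, setting such drifts against the 1.2-point CI width would be unfair, since that width belongs to all 19,000 users and not to one year.

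Fourth, the plan already limits the problem in part. It uses hospital outpatient visits, any NVAF diagnosis before the prescription, and a separate class for unknown indications. Section 10.2 admits that indications may be missing. No correction of national figures by the county result is planned; section 6.1 offers it only as insight. All this stands and reduces the likely size. It does not let the reader see how the error varies by year, and section 10.2 does not connect missing indications with the trend.

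**Conclusion.** The point holds as a cheap improvement, not as an error that invalidates the study. It follows from the decision rule and the data sources, without any assumption about uptake, that missed AF diagnoses cannot affect on/off-label status before 20 November 2012 and can only lower measured on-label use afterwards. A single county difference cannot describe an error with that shape.

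The size is not documented. The figure of about 0.8 points in the first year against about 17.6 in the last rests on 80% capture, 90% correct-indication use, the assumed shift in mix and even AF use over 2012. At 95% capture the last-year error is 4.4 points. The AF figures in section 6.1 (0.3% seen in inpatient care, 2.5% prevalence in one area) suggest that a gap is possible. They are not like for like, however, and leave out hospital outpatient visits.

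On direction, the main effect is to blunt the rule-driven rise in on-label use across the NVAF approval. Only later could it pass for growing off-label use, and the 2013-2014 drift may be as little as 0.3 to 1.6 points.

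**What to change.** In section 7.2:
- Report the county comparison (hospital only against hospital plus primary care) by year of first prescription, at least before and after each approval date, and by indication (hip/knee, NVAF, DVT/PE). Keep the unsplit figure as a summary.
- Show the class of off-label users with unknown indication separately in the yearly series.
- State that the national trend is conditional on hospital ascertainment and should be read beside the county series.

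The dates and county diagnoses needed are already among the data elements in section 6.4, so the cost is a few sentences and tables. The downside is small cells in 2012 and in the county hip/knee stratum (about 103 users in all if spread by population). That stratum needs the check least.

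### Recorded comorbidity in the off-label and unknown stratum is likely understated, and the planned county sensitivity analysis does not check it

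*Protocol*

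**What the plan says.** Protocol 6.1 takes the clinical history of apixaban users from the National Patient Register and describes its coverage: "Inpatient and outpatient hospital data are available through the NPR, but the register does not include information from primary care visits". Primary care records are available for Västra Götaland County only.

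Protocol 6.3 defines on-label use by an adult dispensation to "A patient whose hospital records include" a qualifying procedure or diagnosis. Section 6.2 adds primary care diagnoses for NVAF and DVT/PE where they exist, which means in the one county.

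Protocol 7.2 sets up five strata. Strata 1 to 3 are the labelled indications. Stratum 4 is a list of recorded surgeries and diseases. Stratum 5 is the remainder: "Patients who have no evidence of the conditions for on-label use and who cannot be assigned to the list of pre-defined off-label uses". It is counted as off-label and unknown. The second step of 7.2 then summarises in each stratum, as its item 5, "Select co-morbid conditions/medical history, such as renal impairment, severe hepatic impairment, congenital or acquired bleeding disorders".

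The sensitivity analysis in 7.2 is specified for one quantity: "A sensitivity analysis will compare the proportion of on-label users based on both primary care and hospital data" is set against the proportion from hospital data alone, within the county. Section 10.2 acknowledges that possible indications may be missing and does not mention comorbidity.

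**The concern.** One incomplete source does two jobs. It decides whether a patient lands in stratum 5, and it supplies the comorbidity then tabulated for that stratum. A patient managed only in primary care has no qualifying hospital diagnosis, so is placed in stratum 5, and has no hospital record of renal impairment or a bleeding disorder either. Ascertainment of the characteristic is thus tied to membership of the group.

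Objective 2 is to describe the characteristics of on-label and off-label users, and section 1.1 calls use outside the indications a regulatory and safety concern. A low rate of renal impairment or bleeding disorder in stratum 5 could be taken as a finding about those patients when it partly reflects records that the register does not hold. Nothing in the specified analyses would show how much.

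**Working it through.** **The plan's own figure.** The only statistical figures are the interval widths in Table 2. With full width = 2 × 1.96 × √(p(1−p)/19,000), p = 5, 15, 25, 35 and 45% gives 0.620, 1.015, 1.231, 1.356 and 1.415 percentage points. These round to the stated 0.6, 1.0, 1.2, 1.4 and 1.4. Table 2 is right, but it describes sampling error in the off-label proportion and does not bear on this point.

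**The sections side by side.**
- Source of diagnoses nationwide: the National Patient Register (6.1). The data elements in 6.4 add primary care codes for the county and dispensed drugs, but no other nationwide diagnosis source.
- Entry to strata 1 to 4: a recorded procedure or diagnosis (6.2, 6.3, 7.2).
- Entry to stratum 5: none recorded (7.2).
- Comorbidity row: reported for every stratum (7.2, item 5).
- Check on missing primary care data: on-label proportion only (7.2).

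**Illustration.** The Protocol gives no capture rates, so every input here is an assumption:
- h = probability of any hospital contact: 0.6, 0.8, 0.9
- s_i = capture of the indication given contact: 0.8, 0.95
- s_c = capture of the comorbidity given contact: 0.8
- L = true on-label share: 0.6, 0.8, 0.9
- true comorbidity: 15% in on-label users and m × 15% in off-label users, with m = 1, 2, 3
- true comorbidity does not depend on hospital contact.

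Patients whose indication is recorded have their comorbidity captured with probability s_c. Stratum 5 has share 1 − h·s_i, and only the part h(1 − s_i) has any hospital contact. Capture in stratum 5 is therefore s_c × r, with r = h(1 − s_i)/(1 − h·s_i). This r is below 1 whenever h is below 1.

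With m = 1, recorded comorbidity is 15% × 0.8 = 12.0% in on-label users and in stratum 4. In stratum 5 it is 12.0% × r:

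| h | s_i | r | Stratum 5 recorded |
|---|---|---|---|
| 0.6 | 0.80 | 0.12/0.52 = 0.231 | 2.8% |
| 0.6 | 0.95 | 0.03/0.43 = 0.070 | 0.8% |
| 0.8 | 0.80 | 0.16/0.36 = 0.444 | 5.3% |
| 0.8 | 0.95 | 0.04/0.24 = 0.167 | 2.0% |
| 0.9 | 0.80 | 0.18/0.28 = 0.643 | 7.7% |
| 0.9 | 0.95 | 0.045/0.145 = 0.310 | 3.7% |

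**Does this carry over to all off-label users?** Take h = 0.9, L = 0.8, s_i = 0.95, m = 2.
- Stratum 4: weight 0.855 × 0.2 = 0.171; recorded 30% × 0.8 = 24.0%.
- Stratum 5: weight 0.145; true 15% × (0.8 + 0.2 × 2) = 18.0%; recorded 18.0% × 0.8 × 0.310 = 4.47%, that is 4.5%.
- Pooled: (0.171 × 24.0 + 0.145 × 4.47)/0.316 = 15.0%, against 12.0% in on-label users.

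Here off-label users together look sicker than on-label users, while stratum 5 is far below its true value. Over the 54 combinations the pooled off-label figure exceeds the on-label figure in 18, all with m = 2 or 3.

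Stratum 5 itself can also exceed the on-label figure. With h = 0.9, L = 0.6, s_i = 0.8, m = 3 it records 15% × (0.6 + 0.4 × 3) × 0.8 × 0.643 = 13.9% against 12.0%, but its true value is 27.0%. What holds in all 54 is the understatement of stratum 5 against its own truth.

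**The case against.** **Stratum 5 is not all off-label use.** A reader might infer that off-label users as a whole will look healthier by construction. The documents do not support that. Stratum 4 is entered through a recorded surgery or disease, and NVAF or DVT/PE patients prescribed apixaban before approval are off-label with a recorded diagnosis. The pooled direction depends on the mix and on true differences. This objection stands in full.

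**Stratum 5 lacks qualifying diagnoses, not hospital records.** A patient with only a renal or hepatic hospital code could be in it with that code visible, and the register covers hospital outpatient visits since 2001. Severe hepatic impairment may be mostly hospital-recorded. This stands as a limit on size: the effect will differ by condition.

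**Item 5 names no source, and 6.4 leaves coding to the SAP.** True, but coding cannot recover diagnoses that the register does not hold. The sources, the rule for stratum 5, the summary by stratum and the scope of the county comparison are all fixed in the Protocol.

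**The gap is already disclosed.** Section 6.1 says that the county data will give greater detail and some insight into missing primary care data. The comparison actually specified is still confined to the on-label proportion, and 10.2 to indications.

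**The study is descriptive, and stratum 5 is labelled unknown.** No between-stratum test or safety conclusion is planned, so harm depends on how the tables are read. That lowers the weight of the point. It does not remove it, because stratum 5 counts as off-label and gets its own comorbidity row.

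**Any ratio is only assumed.** Capture of 60% to 80% in strata 1 to 4 and 20% to 40% in stratum 5 would give a ratio of 0.60/0.40 = 1.5 to 0.80/0.20 = 4. That only returns the assumptions and is no estimate.

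**Conclusion.** The point holds for stratum 5. Its recorded comorbidity is likely understated relative to strata 1 to 4, because the same register gap drives both stratum membership and comorbidity capture. Neither the specified county comparison nor 10.2 covers this.

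The size is unknown. The recorded 0.8% to 7.7% against 12.0% above shows the mechanism under assumed contact and capture rates, with true comorbidity unrelated to hospital contact. If patients seen only in primary care are truly less ill, part of a low figure would be real. If nearly all users have hospital contact, the understatement shrinks, and at h = 1 it vanishes in this model.

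The on-label proportion is not touched by this point. Nor are items read from dispensing data: dose, concomitant drugs, earlier anticoagulants and prescriber specialty. The exposure is the comorbidity part of Objective 2, which merits a change at modest priority.

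**What to change.** 1. In 7.2, extend the Västra Götaland sensitivity analysis to the selected comorbidities. Among county patients, fix the stratum by hospital data and tabulate each comorbidity by stratum twice: from hospital data only, and from hospital plus primary care data. Fixing the stratum keeps some patients in stratum 5 whom primary care data would show to be on-label. That is intended, because the nationwide stratum 5 is defined in the same way and the difference then isolates comorbidity capture. Reclassification is already covered by the planned comparison of proportions.
2. In the Objective 2 tables, report stratum 5 separately from known off-label use.
3. In 10.2, add that hospital-based comorbidity in stratum 5 is likely under-ascertained and should not be read as a lower true prevalence than in the other strata.

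A row with the number of hospital contacts by stratum would help but is optional. Dispensed-drug markers of comorbidity are not recommended, since none are specified for these conditions.

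The cost is a few extra tables from data already listed in 6.4. County estimates are less precise, and carrying them to the whole country needs the representativeness that 7.2 already assumes.
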